For all extended assessment periods, upon completing the main assessment, participants will be invited to participate in an optional assessment consisting of measures that were not included in the main assessment due to concerns regarding assessment length and participant burden. The optional assessment should take approximately 20-30 minutes to complete, and consists of questions regarding further responses to pain, goals, and future expectations. Optional outcome assessment data will be recorded on an electronic case report form in REDCap.

Participants are informed all optional assessments are completely voluntary, and that they may refuse to complete the optional assessments (or stop them at any time) with no effect on their payment for their completion of that particular assessment period. Participants will be informed they will not be compensated for completing the optional assessments.

D6i. Re-Assessment of Pain Interference

A participant's level of chronic pain interference for general activities will be re-assessed following consent and enrollment into the study to ensure that pain interference still meets study entrance criteria. Participants will be asked the exact same screening question they were asked initially, and a participant must answer with a pain interference score of ≥ 3 for general activities within the past 3 months to remain in the study. Participants who score less than 3 will be thanked for their time and withdrawn from the study.

The same pain consistency and pain frequency questions that were asked at screening will be re-assessed during the Pain Interference Re-Assessment. If inclusion criteria for pain consistency and frequency are not met at re-assessment, the participant will be withdrawn from the study.

If the participant's level of pain interference is ≥ 3 at re-assessment (and consistency/frequency criteria are also met), study staff will also administer an additional measure of pain interference, the Roland Morris Disability Questionnaire (RMDQ). The participant's score on the RMDQ will be used as one of the strata for randomization.

These two assessments of pain interference may be completed up to 7 weeks before the start of treatment. Participants will not be compensated for completing these assessments.

D6j. General EMA and ActiGraph Monitoring

EMA Surveys

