Participants who are not randomized will be asked to mail back any ActiGraphs still in their possession. Randomization will use a covariate-adaptive randomization scheme. We will use a procedure proposed by Pocock and Simon (see Chapter 9 of Randomization in clinical trials: Theory and practice, 2nd edition, 2016, by W.F. Rosenbeger and J.M. Lachin, John Wiley and Sons), with the objective of balancing the covariate in the marginal distributions. The covariates for the covariate-adaptive randomization will be sex, baseline pain interference score (mild/moderate or severe), and low back pain (LBP) type (primary or secondary pain).

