We will monitor session attendance and session dates to track percentage of attendance and to account for absenteeism and reasons for any missed sessions. Reasons for attrition will be assessed for participants who withdraw. Given clinician-rated participant engagement during sessions was associated with dropout in our preliminary research,³⁸ we will assess this at each session for each participant. Enactment of treatment-specific changes will be assessed by homework practice, assessed via EMA. Comparisons between the treatment conditions in dropout rates will be made, and variables shown to differentiate the groups will be included as covariates.

To minimize possible missed EMA data, we will provide financial incentives for completing the EMA surveys (i.e., \$1.00 per assessment, plus a \$6.00 “bonus” for each week they complete ≥ 12 assessments). In addition, a staff member will monitor the EMA data daily for possible missing responses and employ an internal protocol for contacting the participant regarding missed surveys. This protocol will be strict enough such that participants who are not completing surveys are followed up appropriately, but also allow enough flexibility so that the number of contact attempts is reasonable and will depend on where the participant is in study participation and their unique circumstances. For example, a participant who has withdrawn from treatment due to issues of time commitment but remains intent-to-treat may warrant less frequent contacts about missed surveys compared to someone who remains in treatment and is fully engaged.

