Post-Treatment Monitoring Period*	Fifty-six (56) EMA assessments	Twice daily EMA assessments for 4 weeks following end of treatment	About 5 minutes per assessment	\$1 per completed EMA assessment; \$6 bonus for every week with ≥ 12 completed
Return Activity Monitor	N/A	Once, following end of Post-Treatment Monitoring Period	N/A	\$70
3-Month Extended Assessment	One online or telephone assessment	Once, approximately three months following end of treatment	About 45-60 minutes	\$25
6-Month Extended Assessment	One online or telephone assessment	Once, approximately six months following end of treatment	About 45-60 minutes	\$25

* Participants will wear ActiGraphs for the duration of monitoring periods

D6p. Study Data

We list the demographic and descriptive information we propose to collect from the study participants in the next paragraph. The outcome variables, covariates (variables to control for in planned analyses if needed), and mechanism (mediator and moderator) variables for this study are listed in Table 3. Specific measures by time point are provided in Table 4.

Descriptive/Demographic Variables

All participants will be asked to provide demographic data (age, sex, gender orientation, ethnicity, race, marital status, education, alcohol/drug use, smoking behavior, height and weight, income, household size, disability compensation status, lawsuit status, and employment status). We will also ask about their history of MM, CT, and AS treatment and practice, as well as general chronic pain history (pain duration, pain frequency, pain intensity, other pain sources/types, surgery history, and pain interference with employment). We will also ask questions regarding co-morbid conditions (spinal stenosis and sciatica), pain medication use, and treatment preferences.

Outcome variables, covariates, and mechanism variables

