Exploratory Moderators	Cognitive Abilities Treatment Credibility COVID-19	PROMIS Cognitive Function Abilities (6 items ext. only) Treatment Credibility & Expectancies items (5 items EMA only) Investigator-developed items on COVID-19's effects (6 items ext. & 1 item Qualitative Interview)
Covariate	Primary Problem (LBP primary or secondary)	Baseline Self-Report
Optional Assessments	Responses to Pain Future Self Values-Consistent Goals	Positive & Negative Response to Pain Scales (85 items) Future Self Questionnaire (FSQ) (16 items) Valued Living Scale (VLS) (8 items)
Qualitative Outcomes	Experiences in group & program feedback	15-30" of investigator-developed qualitative items

Table 4. Study Assessment Schedule

Measures	EMA	Baseline	Pre-Treatment	During Treatment	Post-Treatment	3-Month	6-Month
Demographic Information		X					
Pain and Treatment History		X					
Start Back Tool		X					
Pain Medication Questionnaire (PMQ)		X					
Roland Morris Disability Questionnaire SF (RMDQ)		X					
PROMIS Pain Interference	X		X		X	X	X
Pain Appraisal Scale (PAS)	X		X		X	X	X
2-item Catastrophizing Scale from the Coping Strategy Questionnaire (CSQ)			X		X	X	X
Pain-Related Cognitive Process Questionnaire (PCPQ) Non-Judgment Scale	X		X		X	X	X
Godin Leisure-Time Exercise Questionnaire	X		X		X	X	X
Hours Spent Sitting w/o Exercising	X						
Pain Intensity NRS	X	X	X		X	X	X
Positive and Negative Affect Schedule (PANAS)	X		X		X	X	X
PROMIS-29 Sleep Disturbance			X		X	X	X
PROMIS-29 Physical Function			X		X	X	X
PROMIS-29 Depression			X		X	X	X
PROMIS-29 Anxiety			X		X	X	X
PTSD Checklist (PCL-C)			X		X	X	X
Medication & Cannabis Use			X		X	X	X
UW Pain-Related Self-Efficacy Scale	X		X		X	X	X
Participant Engagement				X ^a			
Working Alliance Inventory (WAI)	X ^b						
Group Climate Questionnaire (GCQ-S)	X ^b						
Duration and Times Practicing Skills	X				X	X	X
Sleep/Wake Times	X						
Health Care Utilization			X		X	X	X
Pleasant Events Schedule SF			X		X	X	X
Behavioral Activation for Depression Scale (BADS)			X		X	X	X
Global Quality of Life			X		X	X	X
Employment Status	X	X			X	X	X
Weight	X	X			X	X	X
Mindful Awareness and Attention Scale (MAAS)			X		X	X	X
Pain Resilience Scale			X		X	X	X
Pain-Related Cognitive Process Questionnaire (PCPQ) – Full			X		X	X	X
Control, Harm, Disability, and Medication Scales from the Survey of Pain Attitudes (SOPA)			X		X	X	X
PROMIS Cognitive Function Abilities			X		X	X	X
COVID-19 Impact Questions			X		X	X	X
Treatment Credibility and Expectancies	X ^c						

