At the end of the study when it comes time to conduct data analysis, study investigators (including those unblinded to intervention, such as both co-PIs) may need access to the data, in order to conduct specific analyses. Since (1) no investigators would be able to link any individual participant whose name was heard in fidelity recordings to any study data, and (2) any data investigators (blinded or unblinded) have access to at this point in the project would be locked, it is thus possible for unblinded investigators to also partake in data analysis.

Any staff member listed above may, with discretion from the co-PIs, participate in the actual writing/editing portion of any manuscript(s) that result from this study. During the data collection

phase of the study, blinded staff will not analyze or report data. Once the data is locked, all staff members, unblinded or blinded, may assist with analyzing or reporting data as needed.

D6s. Statistical Analyses

Structural equation modeling (SEM) will be used to evaluate the extent to which early treatment changes in catastrophizing, activity level, and non-judgment predict subsequent late treatment changes in pain interference, and the extent to which these associations are shared across the three treatments, or if some are unique to a subset of the treatments (Aim 1). We will also use SEM to examine the mechanisms of maintenance of gains from post-treatment to follow-up, to address the secondary study aim. Relevant covariates will be tested for and appropriately controlled for (when indicated) across all models. The Hochberg and Benjamini procedure will be used to control for alpha inflation in all analyses. This alpha control procedure involves putting the significance levels of the planned primary analyses in ascending order, and matching them to the actual significance levels obtained with the analyses, also placed in ascending order.

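### Covariates are to be chosen from observed differences with no limit to baseline variables, and the three minimisation factors are not fixed in the primary models

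*Combined protocol and SAP*

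**What the plan says.** Three places govern covariates, and all are conditional on what the data show.

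- D6n, after sentences on attendance, clinician-rated engagement and homework practice: the arms are to be compared on dropout, and "variables shown to differentiate the groups will be included as covariates".
- D6s, opening paragraph: "Relevant covariates will be tested for and appropriately controlled for (when indicated) across all models".
- D6p, introducing Table 3: "covariates (variables to control for in planned analyses if needed". The Covariate row of Table 3 holds one entry, "Primary Problem (LBP primary or secondary").

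None of these gives a candidate list, a threshold, or a restriction to variables measured before randomisation.

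Allocation follows a Pocock and Simon scheme. D6k states: "The covariates for the covariate-adaptive randomization will be sex, baseline pain interference score (mild/moderate or severe), and low back pain (LBP) type". D6i gives the source of the pain interference factor: "The participant's score on the RMDQ will be used as one of the strata for randomization". The text of D6s does not put sex or the RMDQ category into the primary SEMs or into the between-arm ANOVAs of Step 1 and item (5).

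Three of the six primary tests are between-arm differences in the early mechanism slopes (paths a1 and a2). D6s reads non-significant a paths with a significant b path as support for the Shared Mechanisms Model. Significant a paths, with the b path and suitable post hoc results, support the Specific Mechanisms Model.

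**The concern.** There are two separate problems.

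**An open selection rule.** A covariate measured after randomisation and affected by the assigned treatment is not a confounder of the arm effect. Conditioning on it breaks the protection of randomisation whenever it shares causes with the mechanism slope. Nothing in D6n or D6s keeps such variables out. Table 3 classes patient engagement and skills engagement as secondary mechanisms, so the plan itself places them after treatment. D6n also reports that "clinician-rated participant engagement during sessions was associated with dropout in our preliminary research", which makes engagement a natural variable to emerge from a dropout comparison.

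**Design factors left out of the analysis.** Minimisation makes the arms more alike on three factors than chance would. A model that omits them leaves their variance in the residual although it no longer varies freely between arms. The standard error of the arm contrast is then too large.

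Both bear on the a paths, whose significance or non-significance helps decide between the two mechanism models. A false arm difference favours the Specific model; a missed one favours the Shared model.

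**Working it through.** **A. The plan's own figures.** The point disputes none of them.

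- Enrolment (D5, D6u): 240 / (1 − 0.20) = 300, as stated.
- Table 5 rows 4 to 6: F test, f² = 0.15, two tested predictors (the arm dummies), noncentrality 0.15 × N, power 0.80, alpha 0.013, 0.010 and 0.008. Required n is 93, 98 and 102, as stated.
- Table 5 rows 1 to 3: joint significance, r = 0.30, two-sided. Required n is 107, 126, 137 (noncentral F) or 112, 131, 142 (Fisher z), against 109, 129, 140 stated. All are within 3 participants.
- With all three minimisation factors added (5 predictors, 2 tested), rows 4 to 6 remain 93, 98 and 102.

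**B. Selecting a covariate that treatment affects.** Inputs are assumed, because the documents give none. There is no true arm effect. The covariate is shifted in one arm by s SD. An unmeasured cause correlates 0.5 with the outcome and c = 0.3 to 0.7 with the covariate. The simulation used 240 participants, three arms, a 2-df F test at 0.05 and 2,000 runs per setting.

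If the covariate is always included, the bias in the arm contrast is about −(0.5 × c × s):

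- s = 0.3: 0.5 × 0.3 × 0.3 = 0.045 to 0.5 × 0.7 × 0.3 = 0.105
- s = 0.5: 0.075 to 0.175
- s = 0.8: 0.12 to 0.28

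When it is included only if it differs between arms, the simulation gave:

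| Shift s | Covariate selected | Bias (SD) | Rejection under the null |
|---|---|---|---|
| 0 | about 5–6% | about 0 | about 5% |
| 0.3 | 47–49% | −0.02 to −0.07 | 4.6–7.5% |
| 0.5 | 90–91% | −0.08 to −0.17 | 7–19% |
| 0.8 | about 100% | −0.12 to −0.28 | 10–44% |

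The unadjusted test rejected 4% to 6% throughout. The first row is the case of any baseline variable: no bias, and the nominal error rate holds.

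**C. Omitting minimisation factors.** Assumed: three binary factors at 50% prevalence, equal in effect, jointly explaining R² = 10% to 30% of the variance; biased-coin probability 0.8; otherwise as in B.

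Large-sample check with the arms exactly balanced: the 2-df test statistic shrinks by k, the residual variance with all factors divided by the residual variance of the fitted model. The type I error is then 0.05^(1/k).

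- No factors, k = 1 − R²: 0.05^(1/0.9) = 3.6%, 0.05^(1/0.8) = 2.4%, 0.05^(1/0.7) = 1.4%
- Low back pain type only, k = (1 − R²)/(1 − R²/3): k = 0.931, 0.857, 0.778, giving 4.0%, 3.0%, 2.1%

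Simulated results, in the order R² = 10%, 20%, 30%:

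| Model | Type I error | Power, one arm differing by 0.5 SD |
|---|---|---|
| All three factors | 4.8%, 4.9%, 5.6% | 92.4%, 95.5%, 98.5% |
| Low back pain type only | 4.0%, 2.5%, 2.4% | 91.6%, 93.7%, 96.2% |
| None | 3.7%, 2.1%, 1.6% | 90.9%, 92.0%, 94.5% |

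The Monte Carlo standard error near 5% is √(0.05 × 0.95 / 2000) = 0.5 percentage points, so the first row is compatible with 5% and the closed form agrees with the other two. Relative to all three factors, power falls by about 1 to 2.5 points with low back pain type alone and about 1.5 to 4 points with none.

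**The case against.** The strongest reply is that D6n never names attendance, engagement or homework as candidate covariates. They stand in neighbouring sentences about monitoring. Table 3 gives engagement a mechanism role, D6s analyses client engagement in that role, and the only variable in the Covariate row is a baseline one. The groups in the D6n sentence may also be dropouts and completers rather than treatment arms. It would then be ordinary attrition handling, close to the missingness check in D6t.

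Much of this stands. A reader might infer that the plan commits itself to adjusting for treatment-affected variables, but the documents do not say so. What remains is that no sentence excludes them. The dropouts-versus-completers reading does not close the gap either, because engagement is the variable that D6n itself links to dropout.

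A reader might also infer that leaving out the minimisation factors produces false positive arm effects. The working shows the opposite: the test becomes conservative. Nor are the a paths the only randomised contrasts involved, since the Step 1 ANOVA also compares arms and names no covariates.

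Two further replies have weight. Power stays above 90% for a 0.5 SD difference in every model examined, so that loss is modest. Figures 3 and 4 are not shown, and D6s defines a pre-treatment slope for its three-wave model, so the absence of baseline outcome or mechanism terms cannot be asserted. That reply does not supply sex or RMDQ category, which neither the text nor Table 3 names as model covariates.

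**Conclusion.** The concern holds in a conditional form.

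1. The covariate set for the primary models is left to observed differences and is not limited to baseline variables. This can bias the arm contrasts, but only if a treatment-affected variable is selected. Under the assumptions in B the bias is small for a 0.3 SD shift (0.02 to 0.07 SD) and becomes serious at 0.5 to 0.8 SD (0.08 to 0.28 SD, with up to 44% false rejection). If only baseline variables are chosen, the analysis is under-specified but not biased.
2. Of the three minimisation factors, only low back pain type is a listed covariate, and only if needed. Under the assumed 10% to 30% of variance explained, the nominal 5% arm test runs at about 1.6% to 4.0% and loses up to about 4 points of power at 0.5 SD. The direction matters here because a missed arm difference contributes to a Shared Mechanisms conclusion.

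The sizes rest on assumed correlations, shifts, prevalences and variance shares, and on a test at 0.05 rather than the adjusted levels of Table 5. The gaps in the plan do not depend on those assumptions. The change is worth making because it is nearly free.

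**What to change.** - In D6s, name sex, RMDQ-based pain interference category and low back pain type as fixed covariates in every primary SEM and in the between-arm ANOVAs, whatever their observed balance or significance. Align the Covariate row of Table 3 and remove the conditional wording in D6p and D6s.
- Delete the selection rule in D6n, or confine it to a named list of baseline variables in a sensitivity analysis.
- Report dropout by arm descriptively, and use predictors of dropout only in the missing-data model of D6t.
- Optionally, state whether baseline levels of pain interference and of the mechanism also enter each model.

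The cost is a change of wording and a few degrees of freedom. The three factors are already collected for allocation, and rows 4 to 6 of Table 5 keep their required n of 93, 98 and 102.

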The 2-Week Baseline Monitoring Period will consist of an approximately 14-day period before the participant begins his/her first session of treatment. We will schedule all participants to start the Baseline Monitoring Period 14 days before the start of the first group of that cohort. This means, for example, if the first session of CT will be 4/16, the first session of MM will be 4/17, and the first session of AS will be 4/18, all participants will begin the Baseline Monitoring Period on 4/2, which is 14 days before the start of the first group (4/16). Participants will complete Baseline EMA surveys until the day before their first treatment session.

The 2-Week Baseline EMA survey asks questions on pain interference, pain catastrophizing, cognitive processes, average pain intensity during the past 12 hours, mood, pain self-efficacy, sleep/wake times, and activity level and activity monitor wear. On days before Session 1 in the evening EMA there will also be questions on treatment credibility and expectancies. Each EMA survey should take approximately 5 minutes to complete. There are a minimum of 28 EMA surveys for the participant to complete during the Baseline EMA Monitoring Period.

The Treatment Monitoring Period begins on the day the participant is scheduled for Session 1 and ends the day s/he is scheduled for Session 8. The Treatment EMA survey asks the same questions as the 2-Week Baseline EMA survey described above, with the addition of items on therapeutic alliance, group cohesion, and time spent practicing skills learned in treatment. The therapeutic alliance and group cohesion items will be added after the Session 4 and 8 evening EMAs, while the time spent practicing skills items will be asked daily during the evening EMA beginning with Session 1. Additionally, items on treatment credibility and expectancies will be asked once again after Session 1 and before Session 2. While not collected as data, there is also an additional question asked the evening before each treatment session on whether the participant has completed his/her homework activities; this question is used as a reminder to prompt participants to complete their homework activities if they have not already done so.

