Specifically, we propose to evaluate mechanism effects of the three treatments using a 3-wave SEM approach⁹⁸⁻¹⁰². To address Aim 1, we will calculate coefficients representing the linear change in each outcome and mechanism variable during the first two weeks of treatment (early treatment) and second two weeks of treatment (late treatment). To accomplish this, the slope of the regression line for predicting scores from the time variable will be obtained, where the Time variable consists of equally spaced fractions from 0 to 1 for each epoch (i.e., early treatment and late treatment represent two time epochs). While the majority of participants will provide many data points during these time periods, we only need two (representing just 2/24 EMA assessments, or 8% of requested data) ratings in each time period to be able to calculate the slopes for the planned analyses (see below for how any data deemed to be missing at random will be handled using this slope method). To address Aim 1, the time epochs/slopes will be operationalized/calculated as described below:

1. Pre-treatment scores: Slope calculated from EMA ratings/ActiGraph data from all available baseline data (i.e., from days 1-14, see Figure 2).
2. Early-treatment scores: Slope calculated from EMA ratings/ActiGraph data from the first day following the baseline period to mid-treatment (i.e., days 15-28, see Figure 2).
3. Late-treatment scores: Slope calculated from EMA ratings/ActiGraph data from the first day following the mid-treatment mark until the last day of the treatment period (i.e., days 29-42, see Figure 2).

To address the secondary Aim 2, we will calculate slopes from EMA and ActiGraph data across two time periods to compute scores for early and late post-treatment change for the primary outcome (pain interference) and the three mechanism variables (catastrophizing, non-judgment, and activity level), as operationalized below:

1. Early post-treatment scores: Slope calculated from EMA ratings/ActiGraph data from the first day following treatment until 2-weeks following treatment (i.e., from days 43-56, see Figure 2).
2. Late post-treatment scores: Slope calculated from EMA ratings/ActiGraph data from the first day following mid-post-treatment follow-up epoch until the end of the 4-week post-treatment period (i.e., days 57-70, see Figure 2).

Figure 2. EMA data collection and data time points used in analyses

[figure not shown]
[figure not shown]

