Figure 3 below represents the initial model we plan to test for the catastrophizing mechanism variable, providing that it evidences at least a small effect for change for at least one treatment condition during the first two weeks of treatment. However, the model will be simplified (by removing treatment condition as a predictor, and the paths associated with treatment condition) if non-significant treatment effects are found. Up to two additional SEM models will also be tested, with non-judgment and activity level as the foci. Below we describe the specific steps planned to address the study aims and test the primary study hypotheses.

Figure 3. Initial model testing the mechanism role of pain catastrophizing during treatment

Step 1. Ensure at least small time effects (slope) in the early mechanism variables for at least one of the treatment conditions (a requirement for that variable to be considered as a possible mechanism).

- (1) We will perform an initial one-way Analysis of Variance (ANOVA) comparing the pre- to mid-treatment mechanism slopes between the three treatment conditions, separately for each of the three mechanism variables, with a goal of identifying the effect (i.e., Eta squared, η^2) associated with any between group differences in early changes in mechanism variable. If this effect size is < 0.01 , this would indicate a less than small between-group difference in the amount of early treatment change for that mechanism;

this would be interpreted to mean that all three treatment conditions had a similar effect on early treatment change in the mechanism variable.

- (2) In the event that a less than small between condition effect is found, we would then examine the pre- to mid-treatment time effect of this mechanism collapsed across groups to see if this mechanism changes from pre- to mid-treatment (i.e., early treatment). If this effect size (η^2) associated with this time effect collapsed across groups for any mechanism variable is less than 0.01 (representing a small time effect) then there would be evidence that the variable in question is unlikely to act as a mechanism, because at least some change over time early in treatment for that variable, on average, is needed for it to serve as a mechanism.

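### The 14-day slope scores do not cancel a weekly cycle: a weekend difference gives a non-changing participant a slope set by the epoch's starting weekday, zero only for a Sunday start

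*Combined protocol and SAP*

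**What the plan says.** Under D6s (Statistical Analyses), each change score is a regression slope: "the slope of the regression line for predicting scores from the time variable will be obtained". No predictor other than time is named, and the scale on which time is measured is given as follows: "where the Time variable consists of equally spaced fractions from 0 to 1 for each epoch". The epochs are 14 days each: baseline ("i.e., from days 1-14, see Figure 2"), early treatment ("i.e., days 15-28, see Figure 2"), late treatment ("i.e., days 29-42, see Figure 2"), and two post-treatment epochs, the first of which is "i.e., from days 43-56, see Figure 2". D6t (Missing Data) adds that morning and evening slopes are computed separately and averaged.

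Step 1 in D6s admits a mechanism to the SEMs if either of two effects on the early slope reaches an eta squared of 0.01: the three-arm difference, or the time effect pooled over arms. The reason given for the pooled check is "because at least some change over time early in treatment for that variable, on average, is needed for it to serve as a mechanism".

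No epoch is tied to a weekday. D6j (General EMA and ActiGraph Monitoring) starts treatment monitoring on the date of Session 1. Its example gives first sessions on 4/16, 4/17 and 4/18 for CT, MM and AS, with a common baseline start of 4/2. It also says: "Participants will complete Baseline EMA surveys until the day before their first treatment session".

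No weekday or weekend term appears in the slope calculation, the SEMs, the randomization covariates or the missing-data section. D6s has a general sentence on controlling for relevant covariates, but it concerns the models, which are fitted after the slopes exist.

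**The concern.** A 14-day window looks safe against a weekly rhythm because each weekday occurs twice. That protects a mean. It does not protect a slope, because the weekend days are generally not placed symmetrically about the middle of the window. With a Monday start they fall on days 6, 7, 13 and 14, mostly late, and a flat series appears to rise or fall.

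Step 1 compares an observed effect size with a low fixed threshold, and no significance test stands behind it. A calendar artefact could therefore carry a mechanism past the threshold when nothing changed. It could also offset a real change in the opposite direction and cause the mechanism to be dropped. Activity counts are the most exposed, since they are the measure most likely to differ between working days and weekends. The a paths, which separate the Shared from the Specific Mechanisms Model, rest on the same early slopes.

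**Working it through.** **1. Reproduce the plan's slope.** D6t tabulates worked slopes at times 0, 0.25, 0.5, 0.75 and 1, where the sum of squares of time is 0.625. Case 1 (12, 14, 15, 15, 10): (-0.5×12 - 0.25×14 + 0.25×15 + 0.5×10) / 0.625 = -0.75 / 0.625 = -1.2, as printed. The other five tabulated slopes (-4, -11.2, -6.8, -32, -8) also reproduce, so the method is an ordinary least-squares slope.

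**2. Apply it to a flat 14-day series with weekend difference D.** Day k has time (k - 1)/13. The sum of squares of day number about 7.5 is 227.5, so on the 0-to-1 scale Sxx = 227.5/169 = 1.346. With four weekend days at mean position p:

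slope = 13 × 4D × (p - 7.5) / 227.5

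| Start | Weekend days | p | Slope |
|---|---|---|---|
| Mon | 6, 7, 13, 14 | 10 | +0.571D |
| Tue | 5, 6, 12, 13 | 9 | +0.343D |
| Wed | 4, 5, 11, 12 | 8 | +0.114D |
| Thu | 3, 4, 10, 11 | 7 | -0.114D |
| Fri | 2, 3, 9, 10 | 6 | -0.343D |
| Sat | 1, 2, 8, 9 | 5 | -0.571D |
| Sun | 1, 7, 8, 14 | 7.5 | 0 |

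Averaging morning and evening slopes leaves these values unchanged if both carry the same D.

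**3. Size against the 0.01 threshold.** The documents give none of the needed inputs. Assumed, as percentages of mean activity: D = 10, day-to-day SD = 25, SD of true slopes = 10, and no true mean change.

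Variance of an observed slope = 25²/1.346 + 10² = 464.3 + 100 = 564.3 (SD 23.8).

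Pooled eta squared = m² / (m² + 564.3 + v), where m is the mean spurious slope and v the variance of the spurious slopes across start days.

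- All Monday: m = 5.71, v = 0; 32.7/596.9 = 0.055.
- All Tuesday: m = 3.43, v = 0; 11.8/576.1 = 0.020.
- All Wednesday or all Thursday: m = ±1.14, v = 0; 1.31/565.6 = 0.002.
- Evenly Monday to Friday: mean coefficient 0.114, so m = 1.14 and v = 10.4; 1.31/576.0 = 0.002. At D = 20: m² = 5.22, v = 41.8; 5.22/611.3 = 0.009.

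Sensitivity: at D = 5 with all Monday starts, m = 2.86 and eta squared = 8.16/572.5 = 0.014. With a true-slope SD of 30 rather than 10, the slope variance is 464.3 + 900 = 1364.3, and the Tuesday case falls to 11.8/1376.1 = 0.0085.

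**4. Between arms.** Suppose arms of equal size always start on Monday, Tuesday and Wednesday, with the early epoch counted from each arm's own Session 1. The coefficients 0.571, 0.343 and 0.114 have variance (0.229² + 0 + 0.229²)/3 = 0.0348.

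- D = 10: 3.48/(3.48 + 564.3) = 0.006.
- D = 20: 13.9/(13.9 + 564.3) = 0.024.

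**5. Epoch length.** D6s also counts 24 EMA assessments per epoch, which is 12 days at two a day. At 12 days a Monday start gives exactly 0, while Tuesday gives +0.27D and Wednesday +0.46D. A shorter epoch moves the zero to another weekday but does not remove the effect.

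**The case against.** The strongest reply is that this is a small effect enlarged by unfavourable assumptions. Much of that stands. The weekend difference, the CV and the slope SD are all assumed. The value of 0.055 needs every participant in every cohort to start on a Monday, whereas D6l plans 3-5 cohorts a year and D6n says sessions will be offered at different times. Starts spread over Monday to Friday stay below the threshold even at D = 20%.

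A reader might also infer from the D6j example that the arms' early epochs begin on different weekdays, so that the a paths are biased. The documents do not establish this. D6s defines the early epoch in words, as starting when baseline ends, and also in numbers, as days 15-28. D6j gives a whole cohort one Day 1, so on the numbered reading all arms share the same dates and this arm difference is zero. On the other reading, the order of arms must also repeat across cohorts, and the dates in D6j are only an example.

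Nor can one infer that the baseline slope carries the same artefact and would cancel it. In the D6j example, baseline lasts 14, 15 and 16 days for CT, MM and AS. If it is instead cut to days 1-14, its phase is common to all arms while epochs counted from Session 1 are staggered. Either way the phases fail to match in two arms.

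Consequences are bounded too. A false pass at Step 1 only sends the variable to an SEM, where the b path is still tested. Simulation put the spurious b correlation at about 0.01 to 0.06 in absolute value. It assumed mean weekend differences of 0.25 to 0.5 daily SD in both variables, the same range for their SD between people, and a person-level correlation of ±0.5. A false drop needs a true change of similar size and opposite sign.

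What the reply does not remove is the arithmetic. The slope rule has no weekday term, and the general covariate sentence acts too late to correct the scores.

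**Conclusion.** The concern holds as a limited defect in how the scores are built. For six of the seven starting weekdays, a complete 14-day slope turns a weekend difference D into apparent change of up to 0.57D in either direction. Nothing in the plan removes it.

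Whether it matters depends on two things the documents do not give: the size of D and how far start days cluster. On the assumed values, clustering on Monday or Tuesday takes the pooled effect past 0.01, and an even Monday-to-Friday spread does not. The stronger conclusion, that Step 1 or the comparison of arms will be misled, is not supported. The between-arm effect needs the Session 1 reading and a repeated order of arms. Even then it exceeds 0.01 only for a larger weekend difference (0.006 at 10%, 0.024 at 20%). Activity counts are the main exposure. The documents give no reason to expect a material weekend effect in catastrophizing, non-judgment or pain interference.

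**What to change.** Before Step 1 and the SEMs, estimate a weekday/weekend difference for each variable from pooled data over days 1-70. Subtract it from the daily values, then compute the slopes. This matters most for activity counts; apply it to the EMA scores as well, for consistency. It works for participants with few ratings and costs almost no precision. It removes the average weekend effect, which is what moves Step 1 and the a paths, but not individual departures from that average.

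A weekend indicator in each participant's own regression would remove individual effects as well. With complete data it returns exactly zero for a non-changing participant at every start day, and inflates slope variance by 0% (Sunday) to 18% (Monday or Saturday; 1/(1 - 0.154) = 1.18). It is an option only where a participant has enough weekday and weekend ratings, and D6s allows a slope from two.

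State in D6s whether the early epoch is counted from the common Day 1 or from each arm's Session 1, and record the start weekday for each participant. The dates are already collected. The cost is one extra modelling step and, if the per-person term is used, slightly less precise slopes.
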